3.2 Additional Variables of Interest

Variable	Description	Variables and Source	Specifications
----------	-------------	----------------------	----------------

Randomization assignment	hearing aid assignment	assign	Binary 1: unilateral 2: bilateral
Clinical site	Which site - Duke or Vanderbilt?	which_site Character version: which_site_ch	Binary 1: Vanderbilt 2: Duke
GHABP Unaided	Unaided: baseline	Question 2 average, 4 standard scenarios: ghabp_q2_4block_base Question 3 average, 4 standard scenarios: ghabp_q3_4block_base	For questions 2 and 3 (IF they answer yes to question 1), doing this separately by question: 1. Subtract 1, multiply by 25, average answer to question across 4 standard scenarios There are 6 scenarios (4 standard, 2 user-nominated) Note that question 1 just asks if this scenario has happened – participants are only included in the averages if they answer “yes” Lower scores are better for both questions
ECHO	Baseline only Note: this is the “sister” questionnaire to SADL (aided)	Global score: echo_global_base Positive effect subscale: echo_positive_effect_base Service cost subscale: echo_service_cost_base Negative features subscale: echo_negative_features_base Personal image subscale: echo_personal_image_base	Questions 1 – 15 are used. This is scored from 1-7 (or reversed for questions 2, 4, 7, 13). There are 4 subscales: Positive Effect, Service & Cost, Negative Features, Personal Image. For each subscale, the average score is calculated. For the global score, this is the mean of the scores for all items (excluding question 11 if applicable).

			
Higher scores are better (higher expectations).
 
See PCORI Scoring file for more details

TFI	
Tinnitus Functional Index
 
Only at baseline
	
Yes/no: tfiyn
 
Number of TFI questions missing: tfi_num_miss
 
TFI invalid flag: tfi_invalid
 
TFI overall score: tfi_overall_score
	
Non-missing if tfiyn=1
 
Overall score: sum all valid answers, divide by the number of questions with valid answers, multiply by 10
 
If more than 7 items are omitted, the overall score is not valid.
 
8 subscales but only reporting overall score
 
Lower scores are better
 
See PCORI Scoring file for more details

Binaural loudness summation	
Baseline only
 
CSL level right
 
CSL level left
 
CSL level both
	
binaural_r_base
 
binaural_l_base
 
binaural_both_base
	Continuous
Dichotic digit test	
Baseline only
 
Right ear directed
 
Left ear directed
 
Free recall both ears
 
Right ear free recall
 
Left ear free recall
	
dichotic_r_base
 
dichotic_l_base
 
dichotic_free_both_base
 
dichotic_free_r_base
 
dichotic_free_l_base
	Continuous
Hearing Aid Fitting information	
Was RealEar performed?
 
Which WRECD was used?
	
hafitrealrear re_wrecd
 
Ear fit
 
Numeric: hafitwhich
 
Character: ear_fit_ch
	Yes/no for RealEar performed – these should all be “yes” for the initial fitting

	Which ear was fit?		Average/measured for WRECD – these should all be “average” at initial fitting Ear fit: 1=right 2=left 3=both
HA fit audiogram – real ear	65 dB SPL target 65 dB SPL output UCL SPL MPO Report on differences between target and output, UCL and MPO R and L ears (may only have 1 if unilateral) 250 Hz 500 Hz 750 Hz 1000 Hz 1500 Hz 2000 Hz 3000 Hz 4000 Hz 6000 Hz 8000 Hz	Right ear: r_250_targ_out_fit r_250_ucl_mpo_fit r_500_targ_out_fit r_500_ucl_mpo_fit r_750_targ_out_fit r_750_ucl_mpo_fit r_1000_targ_out_fit r_1000_ucl_mpo_fit r_1500_targ_out_fit r_1500_ucl_mpo_fit r_2000_targ_out_fit r_2000_ucl_mpo_fit r_3000_targ_out_fit r_3000_ucl_mpo_fit r_4000_targ_out_fit r_4000_ucl_mpo_fit r_6000_targ_out_fit r_6000_ucl_mpo_fit r_8000_targ_out_fit r_8000_ucl_mpo_fit Left ear: l_250_targ_out_fit l_250_ucl_mpo_fit l_500_targ_out_fit l_500_ucl_mpo_fit l_750_targ_out_fit l_750_ucl_mpo_fit l_1000_targ_out_fit l_1000_ucl_mpo_fit l_1500_targ_out_fit l_1500_ucl_mpo_fit l_2000_targ_out_fit l_2000_ucl_mpo_fit l_3000_targ_out_fit l_3000_ucl_mpo_fit l_4000_targ_out_fit l_4000_ucl_mpo_fit l_6000_targ_out_fit l_6000_ucl_mpo_fit l_8000_targ_out_fit l_8000_ucl_mpo_fit	Take absolute value of the difference between target and output Take difference UCL - MPO Do plots of averages by HA configuration for each ear

Assigned HA 3 Month audiogram (real ear)	65 dB SPL target 65 dB SPL output UCL SPL MPO R and L ears (may only have 1 if unilateral) 250 Hz 500 Hz 750 Hz 1000 Hz 1500 Hz 2000 Hz 3000 Hz 4000 Hz 6000 Hz 8000 Hz	Right ear: r_250_targ_out_3m r_250_ucl_mpo_3m r_500_targ_out_3m r_500_ucl_mpo_3m r_750_targ_out_3m r_750_ucl_mpo_3m r_1000_targ_out_3m r_1000_ucl_mpo_3m r_1500_targ_out_3m r_1500_ucl_mpo_3m r_2000_targ_out_3m r_2000_ucl_mpo_3m r_3000_targ_out_3m r_3000_ucl_mpo_3m r_4000_targ_out_3m r_4000_ucl_mpo_3m r_6000_targ_out_3m r_6000_ucl_mpo_3m r_8000_targ_out_3m r_8000_ucl_mpo_3m Left ear: l_250_targ_out_3m l_250_ucl_mpo_3m l_500_targ_out_3m l_500_ucl_mpo_3m l_750_targ_out_3m l_750_ucl_mpo_3m l_1000_targ_out_3m l_1000_ucl_mpo_3m l_1500_targ_out_3m l_1500_ucl_mpo_3m l_2000_targ_out_3m l_2000_ucl_mpo_3m l_3000_targ_out_3m l_3000_ucl_mpo_3m l_4000_targ_out_3m l_4000_ucl_mpo_3m l_6000_targ_out_3m l_6000_ucl_mpo_3m l_8000_targ_out_3m l_8000_ucl_mpo_3m	Take absolute value of the difference between target and output Take difference UCL - MPO Do plots of averages by HA configuration for each ear
--	---	---	---

4 Statistical Analysis Plan

Analysis: To be completed by December 31, 2024.

4.1 Aim: compare all outcomes between the two arms

Compare the outcomes between the two arms (bilateral hearing aid and unilateral hearing aid) at 3 months.

Analysis: This will be reported for patients who have 3-month scores ("completers"). The primary analysis will be performed using either t-tests or Kruskal Wallis tests depending on whether or not the outcome

distributions appear to be normally distributed. The total score for each survey at 3 months or the benefit score will be used as the outcomes. For GHABP, we will compare the four standard questions (averaged and standardized) for the 4 standard scenarios between the two arms at 3 months for patients who answer "yes" to the first question (if the scenario happens).

The null hypothesis is that the means of the outcomes for the two treatment groups are the same.

$$H_0: \mu_{unilateral} = \mu_{bilateral}$$

Table 1: Distributions of 3-Month Outcomes or Benefit Scores by Assigned Treatment Group

	Unilateral (N=XXX)	Bilateral (N=XXX)	P-Value*
GHABP Aided: In this situation, what proportion of the time do you wear your hearing aid?			XXX
N	XXX	XXX	
Missing	XXX	XXX	
Mean (SD)	XXX (XXX)	XXX (XXX)	
Median	XXX	XXX	
Q1, Q3	XXX, XXX	XXX, XXX	
Range	XXX - XXX	XXX - XXX	
GHABP Aided: In this situation, how much does your hearing aid help you?			XXX
N	XXX	XXX	
Missing	XXX	XXX	
Mean (SD)	XXX (XXX)	XXX (XXX)	
Median	XXX	XXX	
Q1, Q3	XXX, XXX	XXX, XXX	
Range	XXX - XXX	XXX - XXX	
GHABP Aided: In this situation, with your hearing aid, how much difficulty do you now have?			XXX
N	XXX	XXX	
Missing	XXX	XXX	
Mean (SD)	XXX (XXX)	XXX (XXX)	
Median	XXX	XXX	
Q1, Q3	XXX, XXX	XXX, XXX	
Range	XXX - XXX	XXX - XXX	
GHABP Aided: For this situation, how satisfied are you with your hearing aid?			XXX
N	XXX	XXX	
Missing	XXX	XXX	
Mean (SD)	XXX (XXX)	XXX (XXX)	
Median	XXX	XXX	
Q1, Q3	XXX, XXX	XXX, XXX	
Range	XXX - XXX	XXX - XXX	
SADL Global Score			XXX
N	XXX	XXX	

Missing	XXX	XXX
Mean (SD)	XXX (XXX)	XXX (XXX)
Median	XXX	XXX
Q1, Q3	XXX, XXX	XXX, XXX
Range	XXX - XXX	XXX - XXX
HHI-E Change Score		XXX
N	XXX	XXX
Missing	XXX	XXX
Mean (SD)	XXX (XXX)	XXX (XXX)
Median	XXX	XXX
Q1, Q3	XXX, XXX	XXX, XXX
Range	XXX - XXX	XXX - XXX
IOI-HA Total Score		XXX
N	XXX	XXX
Missing	XXX	XXX
Mean (SD)	XXX (XXX)	XXX (XXX)
Median	XXX	XXX
Q1, Q3	XXX, XXX	XXX, XXX
Range	XXX - XXX	XXX - XXX
SSQ Change Score		XXX
N	XXX	XXX
Missing	XXX	XXX
Mean (SD)	XXX (XXX)	XXX (XXX)
Median	XXX	XXX
Q1, Q3	XXX, XXX	XXX, XXX
Range	XXX - XXX	XXX - XXX
Speech and Noise Test: 0 Degrees (Co-located) Change Score		XXX
N	XXX	XXX
Missing	XXX	XXX
Mean (SD)	XXX (XXX)	XXX (XXX)
Median	XXX	XXX
Q1, Q3	XXX, XXX	XXX, XXX
Range	XXX - XXX	XXX - XXX
Auditory Working Memory - Recognition Change Score		XXX
N	XXX	XXX
Missing	XXX	XXX
Mean (SD)	XXX (XXX)	XXX (XXX)
Median	XXX	XXX
Q1, Q3	XXX, XXX	XXX, XXX
Range	XXX - XXX	XXX - XXX
Auditory Working Memory - Recall Change Score		
N	XXX	XXX
Missing	XXX	XXX
Mean (SD)	XXX (XXX)	XXX (XXX)
Median	XXX	XXX
Q1, Q3	XXX, XXX	XXX, XXX
Range	XXX - XXX	XXX - XXX

Average Hours of Hearing Aid Use**At 3-Month Visit: Right Ear**

XXX

N	XXX	XXX
Missing	XXX	XXX
Mean (SD)	XXX (XXX)	XXX (XXX)
Median	XXX	XXX
Q1, Q3	XXX, XXX	XXX, XXX
Range	XXX - XXX	XXX - XXX

Average Hours of Hearing Aid Use

XXX

At 3-Month Visit: Left Ear

N	XXX	XXX
Missing	XXX	XXX
Mean (SD)	XXX (XXX)	XXX (XXX)
Median	XXX	XXX
Q1, Q3	XXX, XXX	XXX, XXX
Range	XXX - XXX	XXX - XXX

*T-test/Kruskal Wallis

We will create boxplots or other figures displaying the distributions of these outcomes by randomization. These figures may supplement or replace Table 1 above.

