4.3 Primary aim: compare APHAB scores between the two arms

Compare the APHAB change scores between the two arms (bilateral hearing aid and unilateral hearing aid) at the end of month 3 vs baseline.

Analysis: This will be done for all randomized patients who have both baseline and 3 month scores (a “completers” analysis). The primary analysis will be performed by linear regression and include randomized assignment and clinical site as covariates.

$$APHAB \text{ change score} = \beta_0 + \beta_1 * \text{treatment} + \beta_2 * \text{site}$$

Table 3: Linear Regression Beta Estimates
Outcome Modelled: APHAB Change Score

Covariate	Beta	95% C.I.	P-Value*
Hearing Aid Assignment (Reference: Bilateral)			
Unilateral	XXX	(XXX , XXX)	XXX
Clinical Site (Reference: Duke)			
Vanderbilt	XXX	(XXX , XXX)	XXX

*Using XXX statistic

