2.3 Data Acquisition

Fill in all relevant information:

Study design	Randomized controlled trial with 2 arms (bilateral hearing aid, unilateral hearing aid) Note: Randomization was stratified by clinical site.
Data source/how the data were collected	Screening information pulled from EHR data Baseline surveys captured via in-person interview and recorded in REDCap
Contact information for team member responsible for data collection/acquisition	All data access is through [REDACTED] [REDACTED]. Questions on data validity will go to PI: [name] ([contact])
Date or version (if downloaded, provide date)	10.17.2024
Data transfer method and date	Direct data extraction from REDCap
Where dataset is stored	REDCap

	Extracted data and analytic datasets are stored on a secure drive in the CRU folder: \\duhs-vclin-nc1\dusom_biostats_fs\Data\BiostatsCore\CRU\Head and Neck\[name]\PCORI_Pro00106077\Data pulls
--	--

Notes: Additional variable details for all variables can be found in the “PCORI Variable Details” Excel file. Scoring details can be found in “PCORI Scoring 20240923”.

For GHABP:

6 total scenarios, 4 standard, 2 user-nominated. Standard scenarios:

1. LISTENING TO THE TELEVISION WITH OTHER FAMILY OR FRIENDS WHEN THE VOLUME IS ADJUSTED TO SUIT OTHER PEOPLE
2. HAVING A CONVERSATION WITH ONE OTHER PERSON WHEN THERE IS NO BACKGROUND NOISE

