3. CARRYING ON A CONVERSATION IN A BUSY STREET OR SHOP
4. HAVING A CONVERSATION WITH SEVERAL PEOPLE IN A GROUP

Unaided questions:

1. Does this situation happen in your life?
2. How much difficulty do you have in this situation?
3. How much does any difficulty in this situation worry, annoy or upset you?

Aided/EMA questions:

1. Did this situation happen in the past few weeks? (GHABP aided) OR Did this situation happen in the last three hours? (EMA)
2. In this situation, with your hearing aid, how much does any difficulty in this situation worry, annoy or upset you? **NOTE: this question is non-standard for the aided GHABP.** We will report on this in a descriptive table but will not include in analyses.
3. In this situation, what proportion of the time do you wear your hearing aid?
4. In this situation, how much does your hearing aid help you?
5. In this situation, with your hearing aid, how much difficulty do you now have?
6. For this situation, how satisfied are you with your hearing aid?

Description:

3 Outcomes, Exposures, and Additional Variables of Interest

3.1 *Outcome(s)*

Outcome	Description	Variables and Source	Specifications
IOI-HA	Note: this is measured only at 3 and 6 months	Total score: ioiha_total_3m	Total score: sum responses to questions 1-7 (should be on a range between 1-5). Item 8 is self-perceived hearing difficulty used for normative purposes

			
(currently not used as part of total score)
 
This is initially coded as 0 to 4 in REDCap – changed to 1-5
 
Currently, we're treating IOI-HA total score as continuous, but this may need to be treated as ordinal.
 
Higher scores are better

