4.1 Aim: compare all outcomes between the two assigned treatment arms

Compare the outcomes between the two assigned treatment arms (bilateral hearing aid and unilateral hearing aid) at 6 months.

Analysis: This will be reported for patients who have 6-month scores (“completers”). The analysis will be performed using either t-tests or Kruskal Wallis tests depending on whether or not the outcome distributions appear to be normally distributed for continuous outcomes. The total score for each survey at 6 months or the benefit score will be used as the outcomes. The Chi-Square test will be used for the APHAB Responder outcomes, with patient counts and relative frequencies reported.

The null hypothesis is that the means of the outcomes for the two treatment groups are the same.

$$H_0: \mu_{unilateral} = \mu_{bilateral}$$

Table 1: Distributions of 6-Month Outcomes or Benefit Scores by Assigned Treatment Group

	Unilateral (N=XXX)	Bilateral (N=XXX)	P-Value*
APHAB Global Change Score			XXX
N	XXX	XXX	
Missing	XXX	XXX	
Mean (SD)	XXX (XXX)	XXX (XXX)	
Median	XXX	XXX	
Q1, Q3	XXX, XXX	XXX, XXX	
Range	XXX - XXX	XXX - XXX	
APHAB Responder (25 Units)**			XXX
No	XXX (%)	XXX (%)	
Yes	XXX (%)	XXX (%)	
Ineligible to Drop 25 Units	XXX	XXX	
APHAB Responder (15 Units)**			XXX
No	XXX (%)	XXX (%)	
Yes	XXX (%)	XXX (%)	

Ineligible to Drop 15 Units	XXX	XXX	
SADL Global Score			XXX
N	XXX	XXX	
Missing	XXX	XXX	
Mean (SD)	XXX (XXX)	XXX (XXX)	
Median	XXX	XXX	
Q1, Q3	XXX, XXX	XXX, XXX	
Range	XXX - XXX	XXX - XXX	
HHI-E Change Score			XXX
N	XXX	XXX	
Missing	XXX	XXX	
Mean (SD)	XXX (XXX)	XXX (XXX)	
Median	XXX	XXX	
Q1, Q3	XXX, XXX	XXX, XXX	
Range	XXX - XXX	XXX - XXX	
IOI-HA Total Score			XXX
N	XXX	XXX	
Missing	XXX	XXX	
Mean (SD)	XXX (XXX)	XXX (XXX)	
Median	XXX	XXX	
Q1, Q3	XXX, XXX	XXX, XXX	
Range	XXX - XXX	XXX - XXX	
SSQ Change Score			XXX
N	XXX	XXX	
Missing	XXX	XXX	
Mean (SD)	XXX (XXX)	XXX (XXX)	
Median	XXX	XXX	
Q1, Q3	XXX, XXX	XXX, XXX	
Range	XXX - XXX	XXX - XXX	

*T-test/Kruskal Wallis or Chi-Square test

**Denominator for percentages does not include patients ineligible to drop 'x' units

We will also describe the distributions of additional variables at 6-month visit as appropriate by assigned treatment (subscales and total scores where change score was reported above). We will also create boxplots for APHAB Global total score and change score by randomization. These figures may supplement Table 1 above.

Table 2: Distributions of Clinical Variables by Assigned Treatment

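### The by-arm secondary tests at 3 and 6 months switch between t-test and Kruskal-Wallis on apparent normality, under a null about means, with no planned arm difference or confidence interval and no use of site or baseline

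*SAP*

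**What the plan says.** The 3-month secondary SAP, section 4.1, sets the test for every continuous outcome in its Table 1: "The primary analysis will be performed using either t-tests or Kruskal Wallis tests depending on whether or not the outcome". The condition for the t-test is that these "distributions appear to be normally distributed". It names no normality test, threshold, graphical rule or blinding of the check. One hypothesis then covers all rows: "The null hypothesis is that the means of the outcomes for the two treatment groups are the same".

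The table shell has a column per arm (N, missing, mean with SD, median, quartiles, range) and a p-value column. Neither text nor shell provides for a between-arm difference or its interval. On the planned plots, the section adds: "These figures may supplement or replace Table 1 above".

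The 6-month SAP, section 4.1, uses the same switch and the same null for its continuous outcomes: "The analysis will be performed using either t-tests or Kruskal Wallis tests depending on whether or not the outcome". Its two responder rows go to a chi-square test. There, figures may only supplement the table.

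Three related statements:
- For IOI-HA, section 3.1 of the 3-month SAP says the team is "treating IOI-HA total score as continuous, but this may need to be treated as ordinal".
- Section 2.3 of both SAPs records: "Note: Randomization was stratified by clinical site". Neither secondary test uses site.
- The primary APHAB SAP, section 4.3, fits a linear regression that will "include randomized assignment and clinical site as covariates", and its Table 3 reports a coefficient, 95% CI and p-value.

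**The concern.** There are three connected gaps.

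1. **The hypothesis can change from row to row.** With two groups, Kruskal-Wallis is the rank-sum comparison. It addresses equality of means only when the two distributions have the same shape. The plan therefore states one null and may test another, on a criterion that is not written down and is applied to the observed outcomes.
2. **No effect estimate is planned.** The protocol (section 3) wants to inform whether a second aid is worth its cost. That turns on how large the difference is and how precisely it is known. The SAP calls these outcomes secondary, but some bear on the protocol's second primary objective, HHI-E most plainly through hearing-related quality of life.
3. **Available information is left out.** Site defined the randomisation strata, and the same-instrument baseline is already needed to form each change score. Neither enters the comparison.

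At stake are the clarity and precision of the randomised comparison on these outcomes.

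**Working it through.** The documents state no sample size, power or significance level for these tests, so there is no figure to reproduce.

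**Rows counted from the table shells**
- 3 months: 4 GHABP + SADL global + HHI-E + IOI-HA + SSQ + co-located speech-in-noise + 2 working memory + 2 hours of use (one per ear) = 13.
- 6 months: APHAB, SADL, HHI-E, IOI-HA, SSQ = 5.
- Change-score rows: HHI-E, SSQ, speech-in-noise, recognition and recall at 3 months (5), plus APHAB, HHI-E and SSQ at 6 months (3) = 8.

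**What is lost if figures replace Table 1 at 3 months.** Table 2 of that SAP gives visit-specific scores for the 5 change-score outcomes, though not the SD of change. It does not contain the four analysed GHABP questions, SADL global, IOI-HA or hours of use. So 13 − 5 = 8 rows lose their only by-arm numbers there.

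**Behaviour of the two tests (simulation).** Assumptions: 350 enrolled 1:1 (protocol sections 4 and 6) with 0-20% loss, so 140-175 per arm (GHABP rows may have fewer); two-sided 0.05; normal or gamma-shaped outcomes; 10,000 trials per cell.

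| Situation, equal means | Kruskal-Wallis rejects | t-test rejects |
|---|---|---|
| Same distribution in both arms | 4.6-5.4% | 4.8-5.3% |
| Normal, SD 20-30% larger in one arm | 5.0-5.6% | about 5% |
| Skew 0.7, same SD ratio | about 5.5-8% | about 5% |
| Skew 1.0, same SD ratio | 6.8-9.6% | about 5% |
| Skew 1.4, same SD ratio | 9.4-17.3% | about 5% |

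**How much the unstated criterion matters.** Three plausible rules were compared at a true shift of 0.25 SD (3,000 trials per cell): Shapiro-Wilk p < 0.05 in either arm, absolute skew above 1 in either arm, and absolute skew above 0.5 in pooled residuals.
- At skew 0.5-0.7 they pick different tests in 76-86% of trials, and significance depends on the rule in about 6%.
- At skew 1.4 they differ in 2-4%, and significance depends on the rule in under 1%.

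**Precision of a planned estimate.** The unadjusted 95% CI half-width in SD units is 1.96 × √(4/N):
- N = 350: 0.21
- N = 280: 0.23

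**Gain from baseline.** Let r be the baseline to follow-up correlation and k the baseline SD divided by the follow-up SD. The variance cut from adding baseline to a change-score comparison is 1 − (1 − r²)/(1 + k² − 2rk).

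| | r = 0.7 | r = 0.5 | r = 0.3 |
|---|---|---|---|
| k = 1 | 1 − 0.51/0.60 = 15% | 1 − 0.75/1.00 = 25% | 1 − 0.91/1.40 = 35% |
| k = 0.8 | 1 − 0.51/0.52 = 1.9% | 1 − 0.75/0.84 = 10.7% | 1 − 0.91/1.16 = 21.6% |

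**Cost of omitting site.** If site explains a share R² of variance, the standard error is too wide by 1/√(1 − R²) − 1. That is 0.5% at R² = 1% and 5.4% at R² = 10%: conservative and small.

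**The case against.** The strongest reply is that little is actually lost. Table 1, if kept, gives N, mean and SD per arm, so any reader can compute an unadjusted difference and CI. At 6 months this always holds. A rank test is also a respectable choice for skewed scores: for a pure shift at skew 1.4 it has more power than the means-based test (0.53-0.63 against 0.39-0.47 at 0.2 SD). The two harms seldom coincide, because the rules agree most where the tests differ most. The primary model itself has no baseline term.

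Much of this stands. A reader might infer that the switching rule inflates false positives in general. It does not: when the arms share a distribution, both tests hold their level. The larger rejection rates need strong skew together with unequal spread, which no document establishes, and they show a mismatch with the stated null rather than a spurious claim of some effect. A reader might also infer that the size of the difference cannot be recovered. As planned it can, crudely. Only the optional replacement of the 3-month table by figures removes it.

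What the reply leaves untouched is that the null and the test may not match, that no criterion is written, that no estimate is pre-planned, and that baseline and site go unused.

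**Conclusion.** The concern holds as a weakness in specification, estimation and precision. In 13 rows at 3 months and 5 at 6 months, the test depends on an undefined look at the data under a null that one of the two tests does not address unless shapes match, and no arm difference or interval is planned.

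Its size is modest. The mismatch with the equal-means null runs from none (normal data) to 9-17% rejection (skew 1.4 with an SD 20-30% larger in one arm). The more dependable gain is in precision: a 15-35% variance reduction in change-score rows if SDs are equal at both visits, or 2-22% if the baseline SD is 0.8 of the follow-up SD. These figures rest on assumed sample sizes, shapes, correlations and a 0.05 level.

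The change is worth making for the 3-month rows. It carries less weight at 6 months, where participants may already have switched configuration and the assigned-arm contrast is correspondingly harder to interpret. The two per-ear hours rows fall outside the proposed model: under protocol section 4 unilateral participants choose which ear is fitted and contribute only one, so that comparison raises a different problem.

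**What to change.** For the 11 rows at 3 months other than per-ear hours, and the 5 continuous rows at 6 months:

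- State one linear regression on assigned arm and site. Add the same-instrument baseline in the 8 change-score rows; since a change score already requires it, no participant is lost. Robust standard errors are optional.
- Report the mean difference with its 95% CI beside the p-value.
- Confirm the stated default that IOI-HA is analysed as continuous.
- Keep the rank test for these same 16 rows (11 + 5) as a labelled sensitivity analysis.

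In section 4.1 of the 3-month SAP, remove the permission for figures to replace Table 1, so that they only supplement it, as at 6 months.

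The cost is SAP wording and a few lines of code. The site term follows the primary model. The baseline term goes beyond it and should be recorded as a deliberate choice. The statistical price is the lower power for a pure shift in strongly skewed data, which the retained rank test makes visible.

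Timing matters. The 3-month data date is 10.17.2024, with analysis due by December 31, 2024. The 6-month data date is 10.28.2024, with the SAP dated 01.07.2025 and analysis due by January 24, 2025. If either analysis has begun, document the change, as the investigator agreement in each SAP requires, and report the originally planned test alongside.

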4.2 Aim: descriptive tables/plots for additional variables

Analysis: we will describe or plot the distributions of additional variables at baseline, hearing aid fit, or 3 month visit as appropriate by assigned treatment. For GHABP, the two unaided (baseline) questions and the one aided (3-month) question (averaged and standardized) will only include patients who answered "yes" to the first question (if the scenario happens). These will be reported across the 4 standard scenarios.

Table 2: Distributions of Clinical Variables by Assigned Treatment

	Unilateral (N=XXX)	Bilateral (N=XXX)
GHABP Unaided: How much difficulty do you have in this situation?		
N	XXX	XXX
Missing	XXX	XXX
Mean (SD)	XXX (XXX)	XXX (XXX)
Median	XXX	XXX
Q1, Q3	XXX, XXX	XXX, XXX
Range	XXX - XXX	XXX - XXX
GHABP Unaided: How much does any difficulty in this situation worry, annoy or upset you?		
N	XXX	XXX
Missing	XXX	XXX
Mean (SD)	XXX (XXX)	XXX (XXX)
Median	XXX	XXX
Q1, Q3	XXX, XXX	XXX, XXX
Range	XXX - XXX	XXX - XXX

GHABP Aided: In this situation, with your hearing aid, how much does any difficulty in this situation worry, annoy, or upset you?

N	XXX	XXX
Missing	XXX	XXX
Mean (SD)	XXX (XXX)	XXX (XXX)
Median	XXX	XXX
Q1, Q3	XXX, XXX	XXX, XXX
Range	XXX - XXX	XXX - XXX

ECHO Global Score (Baseline)

N	XXX	XXX
Missing	XXX	XXX
Mean (SD)	XXX (XXX)	XXX (XXX)
Median	XXX	XXX
Q1, Q3	XXX, XXX	XXX, XXX
Range	XXX - XXX	XXX - XXX

ECHO Positive Effect Subscale (Baseline)

N	XXX	XXX
Missing	XXX	XXX
Mean (SD)	XXX (XXX)	XXX (XXX)
Median	XXX	XXX
Q1, Q3	XXX, XXX	XXX, XXX
Range	XXX - XXX	XXX - XXX

ECHO Service Cost Subscale (Baseline)

N	XXX	XXX
Missing	XXX	XXX
Mean (SD)	XXX (XXX)	XXX (XXX)
Median	XXX	XXX
Q1, Q3	XXX, XXX	XXX, XXX
Range	XXX - XXX	XXX - XXX

ECHO Negative Features Subscale (Baseline)

N	XXX	XXX
Missing	XXX	XXX
Mean (SD)	XXX (XXX)	XXX (XXX)
Median	XXX	XXX
Q1, Q3	XXX, XXX	XXX, XXX
Range	XXX - XXX	XXX - XXX

ECHO Personal Image Subscale (Baseline)

N	XXX	XXX
Missing	XXX	XXX
Mean (SD)	XXX (XXX)	XXX (XXX)
Median	XXX	XXX
Q1, Q3	XXX, XXX	XXX, XXX
Range	XXX - XXX	XXX - XXX

SADL Positive Effect Subscale (3 Months)

N	XXX	XXX
Missing	XXX	XXX
Mean (SD)	XXX (XXX)	XXX (XXX)
Median	XXX	XXX
Q1, Q3	XXX, XXX	XXX, XXX
Range	XXX - XXX	XXX - XXX

SADL Service Cost Subscale (3 Months)

N	XXX	XXX
Missing	XXX	XXX
Mean (SD)	XXX (XXX)	XXX (XXX)
Median	XXX	XXX
Q1, Q3	XXX, XXX	XXX, XXX
Range	XXX - XXX	XXX - XXX

SADL Negative Features**Subscale (3 Months)**

N	XXX	XXX
Missing	XXX	XXX
Mean (SD)	XXX (XXX)	XXX (XXX)

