4.1 Descriptive Characteristics for EMA Surveys

Analysis: We will present the mean with standard deviation (SD), median with interquartile range (IQR), and ranges (min and max) for number of EMA surveys completed. The 0-3-month period and 3-6-month period will be done separately, stratified by baseline assignment and 3M choice, respectively.

Table 1: EMA Summaries

Number of EMA Surveys Completed Before 3 Months	Assigned Unilateral (N=XXX)	Assigned Bilateral (N=XXX)
N	XXX	XXX
Mean (SD)	XXX (XXX)	XXX (XXX)
Median	XXX	XXX
Q1, Q3	XXX, XXX	XXX, XXX
Range	XXX - XXX	XXX - XXX
Number of EMA Surveys Completed After 3 Months	3M Choice – Unilateral (N=XXX)	3M Choice – Bilateral (N=XXX)
N	XXX	XXX

Mean (SD)	XXX (XXX)	XXX (XXX)
Median	XXX	XXX
Q1, Q3	XXX, XXX	XXX, XXX
Range	XXX - XXX	XXX - XXX

4.2 Aim: compare EMA surveys between the two arms in the period between baseline and 3 months, and between 3M choice groups between 3 months and 6 months

For question X, we want to look at the answers to all question X's over the 4 standard scenarios.

Analysis: This will be done using intent-to-treat for patients who have EMA surveys and answer "yes" to the first question (if the scenario happens). The primary analysis will be performed by linear mixed effects models with covariates clinical site and assigned treatment/3M choice, with a separate model for each question. The overall average of within-person means will be reported by treatment arm/3M choice, as well as T-test p-values from the fitted models for the treatment arm/3M choice covariate, where a p-value < 0.05 would indicate a difference in average response between treatment arms/3M choices.

Table 4: Repeated Measures ANOVA Comparing EMA Surveys Across Scenarios in Unilateral and Bilateral Groups

Question & Scenarios	Assigned Unilateral	Assigned Bilateral	P-Value*
	(Overall Mean)	(Overall Mean)	
0-3 Months			
1. In this situation, what proportion of the time do you wear your hearing aid?	XXX	XXX	XXX
2. In this situation, how much does your hearing aid help you?	XXX	XXX	XXX
3. In this situation, with your hearing aid, how much difficulty do you now have?	XXX	XXX	XXX
4. For this situation, how satisfied are you with your hearing aid?	XXX	XXX	XXX
3-6 Months			
1. In this situation, what proportion of the time do you wear your hearing aid?	XXX	XXX	XXX
2. In this situation, how much does your hearing aid help you?	XXX	XXX	XXX

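### Aided GHABP difficulty at 3 months, and the 0-3 month EMA difficulty item, are compared between arms without the matching unaided baseline score, which gives up precision of unknown but possibly useful size

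*SAP*

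**What the plan says.** **3-month SAP, section 4.1.** For the GHABP, "we will compare the four standard questions (averaged and standardized) for the 4 standard scenarios between the two arms at 3 months". The method is stated for all outcomes in the section: "The primary analysis will be performed using either t-tests or Kruskal Wallis tests", chosen by whether the distribution looks normal. There is no covariate. Table 1 has a column for each arm and a p-value column, but no arm difference or confidence interval.

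**The two difficulty items.** The item lists in section 2.3 of the same SAP give the baseline question as "How much difficulty do you have in this situation" and the aided question as "In this situation, with your hearing aid, how much difficulty do you now have". Both are asked for the same four standard scenarios. Both are scored by subtracting 1, multiplying by 25 and averaging over the standard scenarios that the patient says occur. If the response codes run from 1 to 5, this is a 0-100 scale. The standardisation mentioned in 4.1 is this rescaling, not a reference to baseline.

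**What happens to the baseline value.** Section 3.2 already defines it: "Question 2 average, 4 standard scenarios: ghabp_q2_4block_base". Its only planned use in that SAP is descriptive Table 2 of section 4.2, where "the two unaided (baseline) questions and the one aided (3-month) question (averaged and standardized) will only include patients who answered" yes to the opening question for the scenario. Table 2 has no test.

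**EMA SAP, section 4.2.** The comparison uses "linear mixed effects models with covariates clinical site and assigned treatment/3M choice, with a separate model for each question". Site is included; baseline difficulty is not.

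**The concern.** In a randomised comparison of a score that was also measured before treatment, the pre-treatment value is usually the most useful covariate. If baseline and follow-up are correlated, leaving it out widens the interval for the arm effect, and any chance difference in starting difficulty passes partly into the arm difference. Here the baseline value is already collected and scored, so using it costs almost nothing.

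The plan gives no reason for leaving it out. Section 4.8 of the primary SAP drops adjusted analyses, but only for the APHAB change score and the two responder definitions. The GHABP test also ignores site, although randomisation was stratified by site and the primary APHAB model includes it.

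At stake is how sharply the trial can say whether a second aid reduces remaining difficulty in everyday situations. The primary APHAB analysis is not affected.

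**Working it through.** The documents state no sample size, power or precision for GHABP or EMA, so there is no figure of the plan's own to reproduce.

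**Inputs**
- 350 planned patients (protocol section 6), allocated 1:1 (protocol section 4), so n = 175 per arm. This is optimistic: the analysis uses patients with a 3-month score who report at least one scenario.
- Two-sided 0.05. The EMA SAP states a 0.05 threshold; two-sidedness and its use for GHABP are assumptions.
- Correlation r between unaided baseline and aided 3-month difficulty: not given. Assumed range 0.2 to 0.6.

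**Raw comparison (in SD units)**
- SE of the arm difference = sqrt(2/175) = 0.107.
- Difference detectable with 80% power = (1.960 + 0.842) x 0.107 = 0.300. This is a reference effect for the calculation, not one that the plan states.

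**With baseline as a covariate**
- Variance is multiplied by 1 - r², and CI width by sqrt(1 - r²).
- Power at 0.300 SD = Φ(0.300 / (0.107 x sqrt(1 - r²)) - 1.960).

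| r | Variance factor | CI narrower by | Power (raw 80.1%) | Detectable at 80% power |
|---|---|---|---|---|
| 0.2 | 0.96 | 2.0% | 81.7% | 0.293 SD |
| 0.3 | 0.91 | 4.6% | 83.7% | 0.286 SD |
| 0.4 | 0.84 | 8.3% | 86.5% | 0.274 SD |
| 0.5 | 0.75 | 13.4% | 90.0% | 0.259 SD |
| 0.6 | 0.64 | 20.0% | 93.9% | 0.240 SD |

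At r = 0.5 the gain is worth 350 / 0.75 = 467 unadjusted patients. Simulating 4,000 trials of 350 patients at each of two correlations gave variance ratios of 0.90 (r = 0.3) and 0.77 (r = 0.5), in agreement with the formula.

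**With losses.** At 140 per arm (20% loss, assumed), power for the same 0.30 SD effect goes from 70.9% to 72.6% at r = 0.2, 82.6% at r = 0.5 and 88.1% at r = 0.6.

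**Chance imbalance.** At 175 per arm, the 95% range for a chance baseline difference is ±1.96 x 0.107 = ±0.21 SD. The raw comparison carries r times that: 0.04 SD at r = 0.2, 0.105 SD at 0.5 and 0.126 SD at 0.6.

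**Covariate or change score.** A change score has variance 2(1 - r) relative to the raw score, assuming equal SDs: 1.6 at r = 0.2, 1.4 at 0.3, 1.0 at 0.5 and 0.8 at 0.6. Below r = 0.5 it is worse than the planned raw comparison; at r = 0.3, power falls to 66.0%. The covariate form is better than the change score throughout the assumed range.

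**EMA.** These figures do not carry over. They apply to one score per person, whereas EMA has up to 5 prompts a day for a week (5 x 7 = 35). A person-level covariate reduces only the between-person part of the variance. The documents give neither variance component nor the number of responders.

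**The case against.** The strongest reply is that nothing is wrong. A two-group test of randomised arms is valid, and its interval already allows for chance imbalance. The trial is powered on APHAB, with no power claim for GHABP or EMA. All of this stands: the point concerns efficiency, and a reader who inferred that the planned result would be biased would be mistaken.

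The correlation could also be low. The opening questions ask about the patient's life at baseline, the past few weeks for aided GHABP and the last three hours for EMA. Each score averages only the scenarios that occurred, so one person's baseline and follow-up may cover different situations. This stands, and it is why the range starts at 0.2, where the gain is slight.

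Four stronger readings are tempting but unsupported:
- **That all four GHABP comparisons ignore their baseline.** Only difficulty has a direct counterpart; use, help and satisfaction have none.
- **That GHABP should follow HHI-E and SSQ, which use change scores.** A change score could lose precision here.
- **That the EMA SAP intended unaided GHABP as a covariate because its outcome table lists it.** Its activity log records that GHABP was removed, so the entry is probably residual.
- **That the loss can be put in GHABP points using the SD of 25.** That SD is an APHAB planning input and says nothing about GHABP.

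The appeal to ecological outcomes in the protocol's second primary objective fits EMA better than the month-3 GHABP, which is a retrospective questionnaire.

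Finally, a linear model gives up the planned fallback to a rank test for a score built from 25-point steps. Robust standard errors, with the rank test kept as a sensitivity analysis, answer this.

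**Conclusion.** The point holds as a low-cost improvement, not as an error. Aided GHABP difficulty is compared as a raw follow-up score with no baseline or site term, and the 0-3 month EMA difficulty model omits the same baseline value. For GHABP the confidence interval would narrow by about 2% to 20% (13% at r = 0.5). Power for an effect otherwise detectable with 80% power would rise to about 82% to 94%. These figures rest on an assumed correlation of 0.2 to 0.6 and on complete data for 175 per arm. The EMA gain is unquantified.

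One added covariate cannot materially harm precision at this sample size even if the correlation is low. The point does not extend to the other three GHABP questions, to the 3-6 month EMA comparison (by chosen configuration, so not randomised) or to the primary analysis.

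**What to change.** 1. **3-month SAP, section 4.1.** Analyse `ghabp_q5_4block_3m` by a linear model with arm, site and `ghabp_q2_4block_base`, with robust standard errors. Report the adjusted arm difference with its 95% CI. Enter baseline as a covariate; do not form a change score. Keep the planned t-test or Kruskal-Wallis test as a sensitivity analysis.
2. **EMA SAP, section 4.2, 0-3 months only.** Add `ghabp_q2_4block_base` as a fixed covariate in the mixed model for the difficulty question.
3. **Missing baseline.** Replace a missing covariate value with the overall mean across both arms, so that no patient with an outcome is dropped.
4. **Documentation.** Record this as a SAP amendment, and label it post-lock if it is made after the 10.17.2024 data pull.

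The cost is a few lines of SAP text and one model term from data already scored. One GHABP item will be modelled differently from the three that have no baseline counterpart. Some covariate values will be imputed; these should be few, but the documents give no count, so the number should be reported.
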